#### 1.0 BACKGROUND AND RATIONALE

## 1.1 Biliary Tract Cancer - Disease Overview

Biliary tract cancer (BTC) develops as a result of malignant transformation of the biliary tract mucosa and is anatomically classified as intra-hepatic, extra-hepatic (hilar and distal) and gall bladder adenocarcinoma. BTC accounts for 10-15% of all primary liver cancer cases worldwide, and its incidence is rising¹. Advanced BTCs are aggressive tumors with median survival time from diagnosis of less than 12 months², and five-year overall survival (OS) of ~5% despite therapy³. The options for systemic chemotherapy for patients with advanced BTC remain limited with few meaningful improvements over the past decades. Valle et al randomly assigned 410 patients with locally advanced or metastatic BTC to receive gemcitabine with or without cisplatin in the phase III ABC-02 trial². Patients on the gemcitabine cisplatin arm demonstrated an improvement in OS (11.7 versus 8.1 months; hazard ratio (HR), 0.64; 95% CI, 0.52 to 0.80; p>0.001) as compared to the gemcitabine alone arm. This result established the gemcitabine and cisplatin combination as a standard first line regimen for patients with advanced BTC. Durable response rates are infrequent however, and a substantial number of patients progress quickly.

#### 1.2 Role of PARP inhibitors in BTC

DNA damage response (DDR) is a broad term describing several complex pathways responsible for repairing damaged DNA. These known pathways include base excision repair (BER), nucleotide excision repair (NER), mismatch repair (MMR), recombinational repair including homologous recombination (HR) and non-homologous end-joining (NHEJ), and direct repair mechanisms. BER, NER and MMR are mechanisms responsible for repairing single strand breaks (SSB), whereas HR and NHEJ pathways are mechanisms involved in repairing double strand breaks (DSB).

Poly (ADP ribose) polymerase 1 or PARP1 is an abundant nuclear protein heavily involved in the repair of SSB8. In the presence of SSB, PARP1 binds to the damaged DNA, undergoes conformational change and catalyzes the production of PAR which acts as a signal for recruitment of DNA repair factors9. Under normal conditions the dissociation of PARP1 from DNA is required prior to DNA repair completion. In the presence of inhibitors, PARP1 remains bound to SSB generating trapped PARP-DNA complexes, thus blocking repair and replication9. Unrepaired SSB can produce deleterious DSB at the replication forks. In replicating cells, DSB are repaired via HR and NHEJ pathways, However, in cancer cells that are HR deficient (HRD), repair mechanisms for DSB fall to more error prone NHEJ pathways which can lead to cell death. Bryant and Farmer separately demonstrated that BRCA1/2 deficient cells, where the homologous recombination mechanism is defective, were exquisitely sensitive to PARP inhibitors. This has led to many studies investigating the efficacy of PARP inhibitors, both as a single agent and in combination with chemotherapy, in various solid tumors including ovarian, breast, brain, pancreatic and NSCLC. However, to date. HRD signaling and the use of PARPi has not been extensively investigated in BTCs.

Using whole exome-transcriptome sequencing, our pre-clinical data of 53 patients with BTCs revealed 14 pts (26.4%) had biallelic DNA damage repair pathway mutations (ATM, BAP1, MSH2, BRCA1, BRCA2). Of these, 11 had somatic mutations and 3 had germline (MSH2, BRCA1, BRCA2) mutations. Four additional patients were found to have mono-allelic mutations with BRCA1 (somatic), PALB2 (somatic) and ATM (familial). These monoallelic mutations have been shown to increase the risk of cancer development and are involved in DNA DSB repair.

BRCA1 associated protein (BAP1), is a deubiquitinase of histone H2A involved in chromatin remodeling and is recruited to DSB sites. BAP1-/- cells are strikingly sensitive

to ionizing radiation and PARP inhibition (olaparib) relative to BAP1+/- and BAP1+/+  $cell^{25}$ .

In addition, 8 patients had isocitrate dehydrogenase (IDH)1 mutations. Pre-clinical data with IDH1 mutant cells demonstrates reduced capacity to repair DSBs which renders them highly sensitive to PARP inhibition. This concept is currently being evaluated in clinical trial (NCT03212274).

In total, 26 patients (49%) in our cohort had either biallelic somatic and germline (n=14) mutations, or monoallelic somatic or germline (n=4) DDR mutations, or IDH1 mutations (n=8) and may have potentially benefitted from the use of PARPi.

Rucaparib is a small oral inhibitor of PARP1, PARP2, and PARP3, currently FDA-approved in patients with ovarian cancer treated with two or more chemotherapy regimen. A phase II ARIEL2 trial evaluating the efficacy of rucaparib at 600 mg twice daily, demonstrated greatest response in patients harboring germline or somatic BRCA mutations (PFS 12.8 months; 95% CI 9.0-14.7), reduced response rate in those with HRD status by high loss of heterozygosity (PFS 5.7 months; 95% CI 3.6-5.5). Grade ≥3 adverse events included anemia, elevated ALT or AST, and fatigue. A recent phase III clinical trial ARIEL3 of 564 patients demonstrated promising disease control in patients with BRCA mutant ovarian cancer. Median PFS in BRCA mutant arm was 16.6 months (95% 13.4-22.9) compared to 5.4 months (95% CI 3.4-6.7) in placebo arm. In patients with HRD status, median PFS was 13.6 months (95% CI 10.9-16.2) versus 5.4 months (95% CI 5.1-5.6). Similar adverse events were reported in each arm. Rucaparib is currently being evaluated in breast, ovarian, as well as prostate cancer with HRD status (NCT02505048, NCT02952534, NCT02975934).

# 1.3 Role of Checkpoint Inhibitors in BTC

[figure not shown]
The role of cytotoxic immune response against a tumor requires a complex and evolving interaction between immune cell subsets. T-cell activation requires dual signaling from the T-cell receptor and an additional co-stimulatory molecule. The first signal includes binding of the T-cell receptor to antigens presented by antigen presenting cells (APCs). Subsequently, the B7 (CD80, CD86) ligand binds to CD28 which is a co-stimulatory receptor. This signaling leads to T-cell proliferation, cytokine release and upregulation of the immune response. As a result, cytotoxic T lymphocyte antigen 4 (CTLA-4) is upregulated and competes with the CD28 receptor for B7 binding. CTLA-4 has higher affinity than the CD28 receptor and therefore T-cell response is ultimately downregulated. PD-1 is a member of the CD28/CTLA-4 family of T-cell costimulatory receptors that includes CD28, CTLA-4, ICOS and BTLA. PD-1 is expressed on activated T cells, B cells and myeloid cells. There are 2 ligands, PD-L1 and PD-L2 that are specific for PD-1. Once they bind to PD-1, down-regulation of T-cell activation occurs. When the PD-1 ligand binds to the PD-1 receptor, T-cell activation is blocked. CTLA-4 and PD-1 are negative regulators of T-cell response that prevent autoimmunity and allows tolerance to self-antigens. If these interactions are interrupted, the checkpoint is turned off which can lead to enhanced antitumor T-cell activation.

One of the first agents studied in this disease group was pembrolizumab, a humanized monoclonal antibody against PD-1 that is designed to block the interaction between PD-1 and its ligands PD-L1 and PD-L2. Twenty-three PD-L1 positive patients with advanced BTC were enrolled in the KEYNOTE-028 phase 1b trial of pembrolizumab monotherapy. Within this cohort of heavily pretreated patients, an ORR of 17.4% (N=4; 95% CI, 5.0-38.8) was demonstrated and an additional 4 patients had stable disease for a disease control rate of 35%. Adverse events were generally consistent with previously reported safety data for pembrolizumab. There were no treatment-related deaths. Five patients, including all responders, remained on treatment more than 40 weeks. Nivolumab is an

anti-PD1 antibody that is currently FDA-approved as a single agent and in combination with other agents in multiple solid tumors. There is an ongoing phase II clinical trial evaluating the efficacy of single agent Nivolumab in advanced biliary tract cancers (NCT02829918), the results of which has not been reported yet. Other checkpoint inhibitors currently being investigated in this disease group include combination checkpoint inhibitors with chemotherapy (NCT03101566) as frontline therapy.

#### 1.4 Rationale

Patients with advanced, unresectable or metastatic BTC have a poor prognosis despite systemic chemotherapy. The median PFS with first-line gemcitabine and cisplatin is expected to be 8 months. PARP inhibitors have been shown to be effective when used as a single maintenance agent or in combination with conventional chemotherapy in patients with BRCA mutations. PARP inhibitors affect the cells ability to repair single strand breaks and also increase frequency of double strand breaks. Disruption of the DNA damage repair pathways results in increased mutational burden, neoantigens and therefore immunogenicity (see Figure 1). This provides a rationale for combining the use of PARPi such as rucaparib with a checkpoint inhibitor, nivolumab. Preclinical data using combination rucaparib with anti-PD1/ PD-L1 antibodies resulted in greater survival benefit and greater tumor response in BRCA1 null syngeneic model as compared to monotherapy. In a separate study, while the use of PARPi in animal models showed increased PD-L1 expression, the combination of PARPi with PD-L1/PD-1 checkpoint inhibitors showed increased therapeutic efficacy in comparison to each therapy alone.

We therefore hypothesize that following first-line platinum based chemotherapy, rucaparib in combination with nivolumab, will improve progression-free survival and overall survival in BTC patients. We expect greater efficacy in patients with DDR and IDH signatures. These results are expected to have an important positive impact because they will provide evidence guided understanding for further evaluation of the use of PARP inhibitors with an immune check point inhibitor in BTCs.

#### 1.5 Correlative Studies

We will study the BTC tumor biology, DDR and immune signatures through the use of pre-treatment tissue (all sites) as well as on-treatment (for patients at University of Michigan) and post-treatment (optional for patients enrolled at all sites) tumor biopsies. In addition, blood will be collected as detailed in the schedule of events/study calendar. Identification of important biologic subsets of BTC patients (such as DDR, IDH and/or immune signatures) that may have clinical efficacy from rucaparib and nivolumab will be the overarching goal of these translational studies along with developing biologic insights for future therapeutic development. Biologic readouts for PD-1 and other immune response biomarkers will be assessed along with specific markers of tumor infiltrating leukocytes (TILs). Biologic markers and RNA expression will be examined in the context of immunologic correlates, tumor biology, and therapeutic efficacy.

#### 2.0 STUDY OBJECTIVES

# 2.1 Primary Objectives

2.1.1 Determine the PFS rate at 4 months in patients with advanced BTC treated with rucaparib and nivolumab following 1st line platinum based therapy

# 2.2 Secondary Objectives

- 2.2.1 Evaluate the ORR and the median PFS and OS from start of study treatment and start of 1st line platinum therapy in patients with advanced BTC.
- 2.2.2 Evaluate the safety of rucaparib and nivolumab in this patient population.
- 2.2.3 Evaluate the ORR, median PFS and OS in patients with and without DDR and IDH signatures.

# 2.3 Exploratory Objectives

- 2.3.1 To explore biomarkers of response and mechanisms of resistance based on the exploratory analysis of tumor tissue obtained through serial biopsies and blood.
  - a) Levels of PD-L1 (B7-H1), PD-L2, CTLA-4, T cell subset, myeloid-derived cell subset infiltration by immunohistochemistry (IHC) at baseline (for all patients), at 2 months and progression (for patients enrolled at University of Michigan)
  - b) Whole exome genomic and transcriptomic (RNAseq) analysis for tumor biology, DDR and immune signature at baseline and progression
  - c) PBMC collection for immune cell subset analysis including serum for future biomarker analysis

# 2.4 Endpoints Assessment

- 2.4.1 Primary Endpoint Assessment: For the intent-to-treat population the progression-free survival (PFS) rate will be defined as the proportion of patients alive and without radiological or clinical progression (leading to withdrawal from the study) at 4 months and patient replacement as specified in section 5.10.
- 2.4.2 Secondary Endpoint Assessment: Overall response rate (ORR) will be determined as per the combined RECISTv1.1 and irRECIST criteria. The progression-free survival (PFS) will be defined as time from date of treatment to date of radiological or clinical progression (leading to withdrawal from the study), or death from any cause, whichever comes first. PFS1 will be from start of study treatment and will be the primary study endpoint. PFS2 will be from start of 1st line platinum therapy. Overall survival (OS) will be defined from the date of treatment to either date of death or censoring. OS1 will be from start of study treatment. OS2 will be from start of 1st line platinum therapy. Follow-up time will be censored at the date of last disease evaluation. Adverse events and reportable serious events are defined by the study protocol (NCI Common Toxicity Criteria for Adverse Events (CTCAE) v5.0).

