| Statistical
Methodology                   | The investigators intend to enroll patients with stable or responding advanced disease after at least 4 months of 1st line platinum therapy, and expect a large majority of those patients to have previously received between 4 to 6 months of platinum therapy. The sample size of this trial is based on the hypothesis that the expected proportion of patients surviving without progression after 4 months of study treatment will be improved with investigational therapy. We will accrue 32 evaluable patients to this trial. Evaluable patients are compliant with study treatment and observed for progression-free survival events, progression, death, or lack of events following up to 4 months of study treatment. Patients noncomplaint with treatment or lost to follow-up will be replaced. Based on the ABC-02 trial, PFS was estimated to be 72% and 60% at 4 and 6 months after first line gemcitabine and cisplatin, similar to the initiation point of our study and PFS was 51% and 32% at 8 and 10 months, similar to the end of the treatment period for the primary outcome assessment in this trial. Using a conditional probability argument, combined with the assumption that patient accrual to this study will follow an approximate uniform distribution over the 4 to 6 months of primary therapy for the patients accrued, we can accept the average of the PFS estimates for each period (4-6 months (66%) and 8-10 months (41.5%)) to correspond to our trial time period. We can then standardize the ABC-02 PFS data so that the 4-6 month estimate is 100% and the estimate for 4 months thereafter is 63%. For our trial, we hope to improve the PFS rate from 63% for these patients to 85%. With our proposed sample size of 32 patients this trial will have 80% power to detect this difference significantly using a 1-sided test. |

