# 3.1 Eligibility Criteria

Patients must have a pathologically confirmed adenocarcinoma of the biliary tract (intra-hepatic, extra-hepatic (hilar, distal) or gall bladder) that is not eligible for curative resection, transplantation, or ablative therapies. Tumors of mixed histology are excluded.

- 3.1.2 Patients must have received 1st line platinum-based systemic chemotherapy for advanced BTC for 4-6 months (16-24 weeks) without radiologic or clinical progression. Last systemic infusion of 1st line platinum-based therapy may not be more than 4 weeks from study informed consent. Prior peri-operative chemotherapy is permitted provided it was completed > 6 months from start of platinum-based therapy for advanced disease.
- 3.1.3 Prior surgical resection, radiation, chemoembolization, radioembolization or other local ablative therapies are permitted if completed ≥ 4 weeks prior to enrollment AND if patient has recovered to ≤ grade 1 toxicity.
- 3.1.4 Patients must have measurable disease (as per RECISTv1.1) in at least one site not previously treated with radiation or liver directed therapy (including bland, chemo- or radio-embolization, or ablation) either within the liver or in a metastatic site unless the patient has had complete response to 1st line platinum-based therapy.
- 3.1.5 Age≥18 years
- 3.1.6 Child-Pugh score of A or B7
- 3.1.7 ECOG performance status of 0-1
- 3.1.8 Ability to understand and willingness to sign IRB-approved informed consent
- 3.1.9 Available archived tissue (FFPE block or 20 unstained slides from prior core biopsy or surgery)
- 3.1.10 Must be able to tolerate CT and/or MRI with contrast
- 3.1.11 Adequate organ function obtained ≤ 2 weeks prior to registration

| absolute neutrophil count | ≥ 1500/mm                      |
|---------------------------|--------------------------------------------|
| hemoglobin                | ≥ 9 g/dL                                   |
| platelets                 | ≥ 100,000/mm                   |
| serum creatinine          | ≤ 1.5 x ULN                                |
|                           |                                            |
| albumin                   | ≥ 3.0 g/dL                                 |
| AST/ALT                   | ≤ 3.0 x ULN (≤5 x ULN if liver metastasis) |
| total bilirubin           | ≤ 1.5 x ULN                                |

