# 5.9 Off Study Criteria

Patients can be taken off study treatment at any time at their own request, or they may be withdrawn at the discretion of the investigator for safety, behavioral or administrative reasons. The reason(s) for discontinuation from study treatment/study participation will be documented and may include:

- **5.9.1** Patient withdraws consent (termination of treatment and follow-up);
- **5.9.2** Loss of ability to freely provide consent through imprisonment or involuntary incarceration for treatment;
- **5.9.3** Patient is unable to comply with protocol requirements;
- **5.9.4** Treating physician judges continuation on the study would not be in the patients best interest;
- **5.9.5** Patient becomes pregnant (pregnancy to be reported along same timelines as a serious adverse event);
- **5.9.6** Development of second malignancy (except for basal cell carcinoma or squamous cell carcinoma of the skin) that requires treatment, which would interfere with this study;
- 5.9.7 Lost to Follow-up. If a research subject cannot be located to document survival after a period of 2 years, the subject may be considered "lost to follow-up." All attempts to contact the subject during the two years must be documented;
- **5.9.8** Termination of the study by the Sponsor, the University of Michigan or the FDA;
- **5.9.9** Patient completes protocol treatment and follow-up criteria;
- **5.9.10** Treatment delay of more than 28 days from last intended therapy;

**5.9.11** Patient has confirmed progressive disease as per RECISTv1.1/irRECIST criteria and/or, at the discretion of the treating physician, exhibits clinical progression which warrants removal from the study.

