#### 7.0 MEASUREMENT OF EFFECT

# 7.1 Antitumor Effect- Solid Tumors

Immunotherapy drugs such as nivolumab can initially cause inflammation in the early stages of treatment. Immune-related RECIST (irRECIST) utilizes RECISTv1.1 but considers an inflammatory response (or "pseudo-progression") as normal. The main difference between RECISTv1.1 and irRECIST is that patients can stay on trial after the first progressive disease (PD) assessment (as per RECISTv1.1) if using immune-related RECIST criteria. This PD per RECISTv1.1 is then re-labeled as immune related stable disease (irSD) per irRECIST and requires addition of unidimensional measurements of all new lesions (that meet the definition of target lesion) to be added to the sum of longest diameters (SLD) calculation for response assessment. Importantly, immune-related progression (irPD) must be confirmed by a follow-up scan at least 4 weeks (within 4-8 weeks) following the initial PD/irSD assessment in order to take the patient off the trial.

Subjects that are deemed to have clinical progression and unstable should not be continued on therapy after PD (per RECISTv1.1) and are therefore not required to have repeat tumor imaging for confirmation as per irPD definition. It is at the discretion of the site investigator whether to continue a subject on study treatment until repeat imaging is obtained. This clinical judgment decision by the site investigator should be based on the subject's overall clinical condition, including performance status, clinical symptoms, and laboratory data.

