# 7.1.6 Progression-Free Survival

Progression-free survival (PFS) is defined as the duration of time from start of treatment to time of progression.

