#### 11.2 Sample Size and Accrual

The investigators hope to enroll patients after 4-6 months of first line platinum therapy without progression. The sample size of this trial is based on the hypothesis that we will improve upon the expected proportion of patients surviving without progression after 4 months of investigational therapy. We will accrue 32 evaluable patients to this trial. Evaluable patients are compliant with study treatment and observed for progression-free survival events, progression (requiring study discontinuation), death, or lack of events at 4 months. Patients non-complaint with study treatment or lost to follow-up (either not secondary to toxicity) will be replaced. Based on the ABC-02 trial, PFS was estimated at 72% and 60% after 4 and 6 months of first line gemcitabine and cisplatin, similar to the initiation point of our study. PFS was 51% and 32% at 8 and 10 months, similar to the end of the treatment period for the primary outcome assessment in this trial. Using a conditional probability argument, combined with the assumption that patient accrual to this study will follow an approximate uniform distribution over the 4 to 6 months of primary therapy for the patients accrued, we can accept the average of the PFS estimates for each period (4-6 months (66%) and 8-10 months (41.5%)) to correspond to our trial time period. We can then standardize the ABC-02 PFS data so that the 4-6 month estimate is 100% to correspond to the start point for patients in this trial and the estimate for 4 months thereafter, 63% (0.415/0.66). For our trial, we hope to improve the PFS rate from 63% for these patients to 85%. With our proposed sample size of 32 patients this trial will have 80% power to detect this difference significantly, with 5% type 1 error, using a 1sided test

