#### 11.4 Data Analyses Plans

The primary endpoint is the progression-free survival proportion measured after 4 months of study treatment for patients in the IIT population. This endpoint is defined as the proportion of evaluable patients alive and progression-free after 4 months of study treatment in the event of no loss to follow-up and/or early patient discontinuation. The outcome is expected to be observed for each patient. In the event that either loss to follow-up or early discontinuation occurs (either not secondary to toxicity), the 4-month PFS will be estimated using the product-limit method of Kaplan and Meier. Follow-up time will be defined as time from the date of first study treatment (PFS1) and 1st line platinum-based therapy (PFS2) until the date of radiological (as per combined RECIST v1.1 and irRECIST criteria) or clinical progression (leading to withdrawal from the study treatment), or loss to follow-up due to toxicity or non-compliance with study procedures, or death from any cause, whichever comes first. Follow-up time will be censored at the date of last disease evaluation. Estimates for the median and 75th percentiles with 95% confidence intervals will be reported. In order to adjust for the patient's exposure to primary platinum-based therapy, a secondary analysis will utilize the Cox proportional hazards model with exposure time entered as an adjustment covariate as either a continuous covariate or as 4 months of exposure versus more than 4 months of exposure. OS will be similarly estimated and summarized with follow-up time calculated from the date of first study treatment (OS1) and 1st line platinum-based therapy (OS2) until date of death or censoring. ORR will be determined as per the irRECIST guidelines for the IIT population. Other safety data (e.g., laboratory safety parameters, vital signs, and new physical examination findings) will be summarized descriptively for the IIT population by reporting counts and percentages, with exact binomial confidence intervals where appropriate. Adverse events will be reported per the NCI Common Toxicity Criteria for Adverse Events (CTCAE) version 5.0.

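### The primary 4-month PFS event is worded inconsistently and has no dating rule, so a first PD on the second scan can be scored progression-free against an unadjusted 63% null

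*Combined protocol and SAP*

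**What the plan says.** The primary event is described in five places, and the descriptions differ.

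- **2.4.1** (primary endpoint): the "proportion of patients alive and without radiological or clinical progression (leading to withdrawal from the study) at 4 months". The parenthesis can be read as covering both kinds of progression or clinical progression only.
- **11.2** (within the definition of evaluable patients): "progression (requiring study discontinuation), death, or lack of events at 4 months". Here the condition follows progression of any kind.
- **11.4** (analysis plan): follow-up ends at "radiological (as per combined RECIST v1.1 and irRECIST criteria) or clinical progression (leading to withdrawal from the study treatment"). Here the condition attaches most naturally to clinical progression, and it concerns treatment rather than the study.
- **Synopsis** (also in an evaluability sentence): "observed for progression-free survival events, progression, death, or lack of events following up to 4 months of study treatment". There is no condition.
- **7.1.6**: "Progression-free survival (PFS) is defined as the duration of time from start of treatment to time of progression". It gives no criterion and no condition, and does not mention death.

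On scoring a scan, 7.1 states: "This PD per RECISTv1.1 is then re-labeled as immune related stable disease (irSD) per irRECIST". Table 5 gives the same mapping. Confirmation is by a scan 4-8 weeks later (7.1, 7.1.4.4), and 7.1.4.4 lets patients who meet its criteria stay on treatment meanwhile. Section 5.9.11 takes a patient off study when the "Patient has confirmed progressive disease as per RECISTv1.1/irRECIST criteria and/or, at the discretion of the treating physician, exhibits clinical progression" warranting removal. Imaging is every 8 ± 1 weeks (6.2, note 6). Only duration of response (7.1.5) is tied to the first date on which progression is documented.

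**The concern.** Under combined criteria, one scan can be PD by RECIST v1.1 and irSD by irRECIST. The plan does not say which label makes a PFS event, or whether a confirmed irPD takes the date of the first PD or of the confirming scan. If the event needs withdrawal, or is dated at confirmation, a progression already visible at the landmark drops out of the count.

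The trial's efficacy conclusion is one comparison of a single-arm proportion with 63%. Deferral can only move that proportion upward, and there is no control arm in which it could also act. Two analysts following the text could also classify the same patient differently, which leaves room to choose a reading after the data are seen.

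**Working it through.** **1. Reproduce the plan's own figures (11.2).** Null: 0.415/0.66 = 0.629, rounded to 0.63. Alternative 0.85, n = 32, one-sided 5%. The plan names neither the test nor the cutoff. Assuming an exact binomial test:

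- P(X ≥ 25 | 0.629 to 0.63) = 0.051 to 0.052, just over 5%.
- P(X ≥ 26 | 0.629 to 0.63) = 0.021 to 0.022, so 26/32 is the smallest cutoff within 5%.
- P(X ≥ 26 | 0.85) = 0.805, matching the stated 80%.

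The null contains no term for confirmation or withdrawal.

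**2. Timing.** Section 3.1.2, on prior chemotherapy, equates months and weeks: "for 4-6 months (16-24 weeks) without radiologic or clinical progression". That makes 4 months 16 weeks. By the calendar it is 4 × 30.44/7 = 17.4 weeks. With scans counted from treatment start:

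| Scan | Due (weeks) | Confirmation, +4 to +8 (weeks) |
|---|---|---|
| First | 7-9 | 11-17 |
| Second | 15-17 | 19-25 |

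Second-scan confirmation always falls after the landmark. If the scan windows accumulate, the second scan is at weeks 14-18 and confirmation at weeks 18-26, still too late. First-scan confirmation falls inside 17.4 weeks. With a 16-week landmark, a first scan done after week 8 could be confirmed between weeks 16 and 17, and a second scan in week 17 is outside the landmark whatever the definition.

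**3. Illustration of size.** Let k be the number of patients with first PD who are scored progression-free. The documents give no value for k. Assume no drug effect and the 26/32 cutoff, with two models:

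- Model A, k patients on average: P(X ≥ 26) at rate p0 + k/32.
- Model B, exactly k rescored in every trial: P(X ≥ 26 − k) at rate p0.

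Ranges cover p0 = 0.629 to 0.63.

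| k | Model A | Model B |
|---|---|---|
| 0 | 0.021-0.022 | 0.021-0.022 |
| 1 | 0.046-0.048 | 0.051-0.052 |
| 2 | 0.094-0.097 | 0.106-0.109 |
| 3 | 0.175-0.179 | 0.193-0.197 |

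**4. Is k = 2 plausible?** Events expected in months 2-4 under the null, from the plan's figures:

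- From the quoted ABC-02 percentages: PFS two months in = ((0.60 + 0.51)/2)/0.66 = 0.841, so (0.841 − 0.629) × 32 = 6.8.
- At constant hazard: √0.63 = 0.794, so (0.794 − 0.63) × 32 = 5.2.

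Two patients are 2/6.8 = 29% to 2/5.2 = 38% of those events. The events also include deaths, clinical progressions and patients stopped at first PD, all of which still count. Two is possible but not established.

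**The case against.** The strongest reply is that the biased scoring needs an unfavourable reading. Section 11.4 is the analysis section, and it most naturally ties withdrawal to clinical progression; the parenthesis in 2.4.1 can be read the same way. The date of radiological progression in 11.4 can mean the date PD was first seen. Survival follow-up runs up to 2 years after treatment, so confirmatory results can be known before the analysis. Continuation under 7.1.4.4 also requires clinical benefit, tolerance, stable performance status and stable or improving markers if expressed, so few patients may be affected.

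Most of this stands, and it limits the point to a missing rule. It does not supply the rule: 11.4 invokes both criteria, Table 5 gives one scan two labels and no date, and 2.4.1 remains open.

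A reader might infer more than the documents support:

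- *That 11.2 scores only progressions that force discontinuation.* Its wording sits in the sentence defining evaluable patients and is not a scoring rule.
- *That the true type I error is about 10%.* This depends on an unstated cutoff and an assumed k. Even the point at which 5% is crossed is unstable: one patient gives 4.6-4.8% or 5.1-5.2% depending on the model, and a 25/32 cutoff gives 5.1-5.2% with nobody deferred.
- *That ABC-02 used ordinary first-PD PFS.* The documents do not give its progression criterion. They show only that the null is unadjusted.
- *That the sample size is wrong.* The 80% power reproduces.

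**Conclusion.** The concern holds as a gap in the definition of the primary endpoint. The wording is inconsistent, no section dates the event, and the scan schedule puts the ambiguity at the 4-month landmark. On a permitted reading, a first PD at weeks 15-17 in a patient kept on treatment is scored progression-free, and the error can run in only one direction.

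Inflation is possible but not demonstrated. The figures of 4.6-5.2%, 9.4-10.9% and 17-20% for one, two and three patients are illustrative: they assume an exact 26/32 cutoff, no drug effect and a chosen number deferred. If confirmed irPD is dated back to first PD, most of the excess disappears. This should be fixed before analysis. Confidence is high that the rule is missing and low on its numerical effect.

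**What to change.** 1. Use one PFS event, progression or death, in the synopsis, 2.4, 7.1.6, 11.2 and 11.4, with no withdrawal condition on radiological progression.
2. Date the event at the first documented PD. If irRECIST is kept, date confirmed irPD back to the first PD and classify second-scan PD only after its confirmatory scan.
3. State that a first PD with no confirmatory scan (for example because of clinical deterioration, death or stopping treatment) is an event at the first PD date.
4. State the landmark in weeks, with a window that includes the scheduled second scan, and keep it consistent with the 4-month null. A scan at weeks 15-17 counted from treatment start fits inside 17.4 weeks; one at week 18, from accumulated windows, does not.
5. Report PFS by the other criterion as a sensitivity analysis. Which criterion is primary is the sponsor's choice.
6. State how CT progression in a patient continuing under Appendix V, item 4c, counts for PFS.

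Separately, 7.1.4.1 measures irPD from the smallest sum since treatment started, while 7.1.4.4 measures it from the initial PD. Because 7.1.4.4 links irPD to stopping treatment, the sponsor must reconcile the two; no clinical rule is proposed here.

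Cost: items 1-6 change wording and analysis only, with no new scans or patients. If irRECIST is kept, classifying second-scan PD may wait up to 8 weeks. If RECIST v1.1 is primary, a true pseudo-progressor counts as an event, which the sensitivity analysis would show. The observed rate may be slightly less favourable.
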